### 5. STATISTICAL ANALYSES

Standard data derivation rules and statistical methods are described in section 10.1 while the study specific data derivation rules and stat methods are described in section 9.

#### 5.1. Disposition of subjects

##### 5.1.1. Analysis of disposition of subjects planned in the protocol

Number of subjects enrolled, vaccinated subjects (at least 1 vaccination, full vaccination course), reason for early withdrawal, FAS, and PPS will be described by vaccine group.

##### 5.1.2. Additional considerations

Not applicable

## 5.2. Demography and baseline characteristics analyses

### 5.2.1. Analysis of demography and baseline characteristics planned in the protocol

Descriptive statistics (mean, standard deviation, median, minimum and maximum) for age, height, weight, and body mass index (BMI) at enrolment will be calculated overall and by vaccine group.

Distributions of subjects by sex, race, ethnic origin will be summarised overall and by vaccine group.

### 5.2.2. Additional considerations

A summary table of important protocol deviations related to COVID-19 will be provided. Also, a listing will be produced.

## 5.3. Primary effectiveness and immunogenicity

### 5.3.1. Analysis of primary effectiveness and immunogenicity planned in the protocol

Refer to [Glossary of terms](#) for definitions of test-based and responder-based vaccine effectiveness. If the co-primary effectiveness objectives for rMenB+OMV NZ are met (Sections [5.3.1.1](#) through [5.3.1.6](#)), then all objectives for MenACWY will be evaluated at 95% CI (Sections [5.3.1.7](#) through [5.3.1.11](#), ref Protocol Section 10.1).

#### 5.3.1.1. Vaccine effectiveness (Test-based): rMenB+OMV NZ - 3 doses (0,2,6-months schedule)

Analysis set: Per-protocol set (PPS) will be the primary analysis population

Statistical method: The VE is defined as  $1 - RR = (1 - \text{percentage of samples without bactericidal serum activity at 1:4 dilution in MenB group} / \text{percentage of samples without bactericidal serum activity at 1:4 dilution in the ACWY group}) \times 100\%$  and it will be analyzed using a generalised linear model with vaccine group, strain, and randomization factors (i.e. region (US/ex-US), age category (10-17 YoA/18-25 YoA), previous MenACWY vaccination (y/n)) as independent variables. Furthermore, a repeated statement will be used to estimate the variance of the RR including correlation within subject's responses to different strains. If the statistical model does not converge due to (one of) the factor(s), a model without this/these factor(s) will be fitted instead. The response variable of the model will be the Bernoulli distributed outcome without bactericidal activity at a 1:4 dilution (i.e. response is 1 if titre  $< 4$ , and 0 if titre  $\geq 4$ ), at 1 month after the last vaccination (Month 7) in the MenB group and at Month 1 for the ACWY group. Each subject will contribute with approximately 35 measures to this analysis, each of the measures corresponding to the response variable to one of the 35 strains randomly assigned to be tested with the samples available for that specific subject.

In order to obtain the VE measure which is a measure based on the relative risk (RR), a generalised linear model will be used with the Binary distribution and link function log in order to compute the log RR and the corresponding 97.5% CI. The obtained values will be exponentiated to obtain the RR and the corresponding 97.5% CI. The VE will be computed as  $100\% \times (1 - RR)$ . Effectiveness of rMenB+OMV NZ (0,2,6-months schedule) will be demonstrated if the lower limit of the two-sided 97.5% CI for VE between MenB and the ACWY group is above 65%.

**5.3.1.2. Effectiveness (Responder-based): rMenB+OMV NZ - 3 doses (0,2,6-months schedule)**

Analysis set: FAS will be the primary analysis population.

Statistical method: The percentage of responders (see definition in [Glossary of terms](#)) and the corresponding exact two-sided 97.5% CI based on Clopper-Pearson method will be calculated [[Clopper](#), 1934].

The objective is to demonstrate that the lower limit of the 97.5% CI for the percentage of responders is higher than 65%.

**5.3.1.3. Vaccine effectiveness (Test-based): rMenB+OMV NZ - 2 doses (0,6-months schedule)**

See Section [5.3.1.1](#)

**5.3.1.4. Effectiveness (Responder-based): rMenB+OMV NZ - 2 doses (0,6-months schedule)**

See Section [5.3.1.2](#)

**5.3.1.5. Vaccine effectiveness (Test-based): rMenB+OMV NZ - 2 doses (0,2-months schedule)**

See Section [5.3.1.1](#)

**5.3.1.6. Effectiveness (Responder-based): rMenB+OMV NZ - 2 doses (0,2-months schedule)**

See Section [5.3.1.2](#)

**5.3.1.7. Lot-to-lot consistency: MenABCWY - ACWY component**

Analysis set: The analysis of lot-to-lot consistency will be based on the PPS.

Statistical method: For each of the three ABCWY lots (Lots 1, 2 and 3 of the MenACWY component of the ABCWY vaccine), GMTs and 97.5% CIs will be calculated by exponentiating (base 10) the least squares means and the lower and upper limits of the 97.5% CIs of the log transformed titres (base10) obtained from an Analysis of Variance

(ANOVA) with factors for vaccine lot and randomization factors (i.e. region (US/ex-US), age category (10-17 YoA/18-25 YoA), previous MenACWY vaccination (y/n)).

Additionally, lot-to-lot GMT ratios will be computed for each pair of ABCWY lots.

Ninety-seven point five percent (97.5%) CIs for the ratios of GMTs will be constructed by exponentiating the difference of the least square means of the log transformed titres and the lower and upper limits of the 97.5% CIs on the difference obtained from the ANOVA model above.

Lot-to-lot consistency criterion: The three ABCWY lots will be considered equivalent if for each of the 4 serogroups A, C, W and Y and each pair of vaccine lots, the two-sided 97.5% CI on the ratio of GMTs at 1 month after the last vaccination will be contained within the interval [0.5, 2.0].

If the co-primary effectiveness objectives for rMenB+OMV NZ are met (Sections [5.3.1.1](#) through [5.3.1.6](#)), then the above will be evaluated at 95% CI.

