**Rationale for blood volume collected:**

In order to provide the necessary serum volume for the bactericidal assays (enc-hSBA and/ or hSBA(s)), 25 mL whole blood will be collected at Visit 2, Visit 4 and Visit 6. At pre-vaccination (Visit 1), 20 mL whole blood will be collected to provide the necessary serum volume for the hSBA.

Blood samples are taken from all subjects irrespective of the testing status in order to maintain the study blind. Refer to Protocol Section 8.4.2.1 for further details.

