#### **5.3.1.8. Immunological non-inferiority: MenABCWY vs. MenACWY**

Analysis set: PPS restricted to subjects without previous ACWY vaccination will be the primary analysis population.

Statistical method: The percentage of subjects with 4-fold rise\*P in hSBA titres against MenACWY indicator strains A, C, W and Y and the corresponding exact two-sided 97.5% CIs based on Clopper-Pearson method will be calculated for the ABCWY (pooled lots) group and the ACWY group [[Clopper, 1934](#)]. The 97.5% CIs for the difference in percentages between ABCWY (pooled lots) and ACWY group will be constructed using the method of Miettinen and Nurminen [[Miettinen, 1985](#)].

Non-Inferiority criterion: Non-inferiority of MenABCWY vaccine for the proportion of subjects with 4-fold rise will be demonstrated if the lower limit of the two-sided 97.5% CI for the difference in percentage of subjects with 4-fold rise between the 2 groups (ABCWY (pooled) lots –ACWY) is above -10%.

\* For the Men A, C, W, Y evaluation, the 4-fold rise is defined as:

- a post-vaccination hSBA titre  $\geq 4$  times the LOD or  $\geq$ LLOQ, whichever is greater, for subjects with a pre-vaccination hSBA titre  $<$ LOD
- a post-vaccination hSBA titre  $\geq 4$  times the LLOQ for subjects with a pre-vaccination hSBA titre  $\geq$ LOD but  $<$ LLOQ, and
- a post-vaccination hSBA titre  $\geq 4$  times the pre-vaccination titre for subjects with a pre-vaccination hSBA titre  $\geq$ LLOQ.

[Table 5](#) reads the LOD and LLOQ of MenACWY indicator strains used in the definition of 4-fold rise provided by the laboratory.

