#### 5.4.1.4. Immune response of MenABCWY, rMenB+OMV NZ and MenACWY

Analysis set: The analysis will be based on the FAS.

Statistical method: The hSBA titres at each time point for all groups (ABCWY group (pooled lots), MenB\_0\_2\_6 and MenB\_0\_6 groups) will be logarithmically transformed (base10) to fulfil the normal distribution assumption. For each *N. meningitidis* serogroup A, C, W and Y and each B indicator strain (M14459, 96217, M13520 and NZ98/254 for fHbp, NadA, NHBA and PorA P1.4 antigens, respectively), the GMTs and GMRs (post-vaccination/baseline) will be obtained from an Analysis of Variance (ANOVA) with factors for vaccine group, region (US/ex-US), age category (10-17 YoA/18-25 YoA), and previous MenACWY vaccination (y/n), and then exponentiating the log-transformed means and their 95% CIs. The ratio of GMTs and GMRs between two groups and the corresponding CI will be estimated additionally.

The total IgG (as measured by ECL) against serogroups A, C, W and Y at baseline (Day 1, Month 0) and

- at 1 month after the first (Day 31, Month 1) and the last vaccination (Day 211, Month 7) for the ABCWY group (pooled lots), and
- at 1 month after the MenACWY vaccination in the ACWY group (Day 31, Month 1),

will be analyzed in a comparable way as described above for hSBA titres. Since total IgG is measured as concentration instead of titer, the resulting geometric mean of the concentrations is abbreviated as GMC.

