## **6. ANALYSIS INTERPRETATION**

Multiple objectives and endpoints require type I error control. Full alpha (0.05) is split equally (alpha=0.025) between rMenB+OMV NZ objectives and MenABCWY objectives. Furthermore, within rMenB+OMV NZ, as well as within MenABCWY, objectives are tested hierarchically. If the first null hypothesis is rejected, then the testing will continue with the second hypothesis at same alpha. Same for 3rd, 4th, and so forth. Whenever a null hypothesis is not rejected, then the testing will stop.

As the comparator for MenABCWY non inferiority objective for the B component will be the selected schedule of rMenB+OMV NZ as determined in this study, the objectives of rMenB+OMV NZ will be analysed first. Additionally, if all null hypotheses related to rMenB+OMV NZ objectives will be rejected, the alpha (alpha=0.025) will be propagated to the MenABCWY part, and hypotheses related to MenABCWY objectives will be tested at full alpha (alpha=0.05). See [Figure 2](#) for an explanation of the hierarchical testing (top to bottom, the order indicated by the arrows).

**Figure 2** Hierarchical testing of hypothesis

\* Alpha split equally between rMenB+OMV NZ and MenABCWY vaccine objectives.

If all rMenB+OMV NZ objectives achieved, MenABCWY vaccine objectives will be tested at full alpha.

\*\* If all objectives of rMenB+OMV NZ are met, the comparator will be the 0,2-months schedule. If the 0,2-months objective is not met, and the 0,6-months is met, then the 0,6-months schedule will be the comparator. If the 0,6-months is also not met, then the 0,2,6-months schedule will be the comparator.

Refer to [Glossary of terms](#) for definitions of test-based and responder-based vaccine effectiveness.

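### The lot-consistency and GMT models leave out the Day 1 hSBA titre that the trial already measures; this gives up some precision but not validity

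*SAP*

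**What the plan says.** **Lot consistency (SAP 5.3.1.7).** GMT ratios come from an ANOVA on log10 titres "with factors for vaccine lot and randomization factors", the latter being region, age category and previous MenACWY vaccination. All 12 ratios (4 serogroups by 3 lot pairs) must have intervals inside 0.5 to 2.0.

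**GMTs and GMRs (5.4.1.4).** These "will be obtained from an Analysis of Variance (ANOVA) with factors for vaccine group", region, age category and previous MenACWY vaccination.

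**Baseline is measured.** Section 3.1, on blood volume, states: "At pre-vaccination (Visit 1), 20 mL whole blood will be collected to provide the necessary serum volume for the hSBA". The 4-fold-rise definitions in 5.3.1.8 and 5.4.1.1 use the pre-vaccination titre, and the GMR in 5.4.1.4 divides by it.

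**4-fold-rise decisions.** In 5.3.1.8 the population is the PPS without previous ACWY vaccination, and "The 97.5% CIs for the difference in percentages between ABCWY (pooled lots) and ACWY group will be constructed using the method of Miettinen" and Nurminen, with no stratification stated. Section 5.4.1.1 uses the same method at 95%. The remaining randomisation factors enter only the identity-link binomial sensitivity models: region and age in 5.3.2.8; region, age and previous MenACWY in 5.4.2.1.

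**Alpha (Section 6).** "Full alpha (0.05) is split equally (alpha=0.025) between rMenB+OMV NZ objectives and MenABCWY objectives", which gives 97.5% intervals, or 95% if every rMenB+OMV NZ objective is met.

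**The concern.** A pre-vaccination titre is usually the natural covariate for a post-vaccination titre. Here it is collected in the same subjects with the same assay, so leaving it out saves nothing. Lot consistency is the place where this could count, because one failure among 12 intervals fails the objective. The comparison with MenACWY has the least precision to spare, resting on about 137 evaluable controls before the restriction to unprimed subjects.

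The plan is also uneven. The randomisation factors are in the decision models for test-based effectiveness (5.3.1.1) and for lots (5.3.1.7), but not in the decision intervals for 4-fold rise, and no reason is given.

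**Working it through.** **Inputs from the SAP.** Section 3.3 gives 548 randomised per lot, 183 in ACWY and 25% drop-out. Reproduced: 548 × 0.75 = 411; 183 × 0.75 = 137.25, stated as 137; pooled lots 3 × 411 = 1233. The margins are 0.5 to 2.0 for lots and -10 points for 4-fold rise. For a two-sided 97.5% interval z = 2.2414.

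**Assumed, because the SAP gives no values.** SD of log10 titre 0.6 to 1.0; correlation rho between Day 1 and post-vaccination titre, within the strata already in the model, 0 to 0.5; 4-fold-rise rates by stratum; share of unprimed subjects.

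**1. Width of the lot-ratio interval.** SE = SD × sqrt(2/411) × sqrt(1 - rho²), with sqrt(2/411) = 0.0698. The interval is the ratio multiplied and divided by 10^(z × SE). The width multiplier sqrt(1 - rho²) is 0.980 at rho 0.2, 0.954 at 0.3 and 0.866 at 0.5. Example at SD 0.6: 10^(2.2414 × 0.6 × 0.0698) = 1.241 without baseline, 1.229 at rho 0.3 and 1.206 at rho 0.5. A simulation of ANOVA against ANCOVA agreed (1.230 and 1.206).

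**2. Effect on the lot decision.** Power per pair with equal lots is 2Φ((log10 2 - z × SE)/SE) - 1. The lower bound over 12 comparisons is 1 - 12 × (1 - power per pair). For a true ratio of 1.4, power is Φ((log10 2 - log10 1.4 - z × SE)/SE).

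| SD | rho | CI factor | Power per pair, equal lots | Lower bound, all 12 | Power per pair, true ratio 1.4 |
|---|---|---|---|---|---|
| 0.6 | 0 | 1.241 | 1.0000 | 1.000 | 0.928 |
| 0.6 | 0.5 | 1.206 | 1.0000 | 1.000 | 0.979 |
| 0.8 | 0 | 1.334 | 0.9984 | 0.981 | 0.703 |
| 0.8 | 0.3 | 1.316 | 0.9994 | 0.992 | 0.748 |
| 0.8 | 0.5 | 1.283 | 0.9999 | 0.999 | 0.832 |
| 1.0 | 0 | 1.433 | 0.9619 | 0.543 | 0.492 |
| 1.0 | 0.3 | 1.410 | 0.9775 | 0.730 | 0.534 |
| 1.0 | 0.5 | 1.366 | 0.9939 | 0.927 | 0.627 |

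At 95% confidence and SD 1.0 the 12-comparison bound is 0.778, 0.876 and 0.970 at rho 0, 0.3 and 0.5.

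**3. Stratifying the 4-fold-rise interval.** Take two equal strata and a true difference of zero. The width ratio is sqrt(mean within-stratum p(1 - p) / pooled p(1 - p)). For 70%/90%: sqrt(0.15/0.16) = 0.968. The half-width with 1233 v 137 is 2.2414 × sqrt(0.16 × (1/1233 + 1/137)) = 8.07 points.

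| Stratum rates | Width ratio | Half-width, 1233 v 137 | Power, 1233 v 137 |
|---|---|---|---|
| 88% / 92% | 0.998 | 6.06 to 6.04 | 0.928 to 0.929 |
| 85% / 95% | 0.986 | 6.06 to 5.97 | 0.928 to 0.935 |
| 70% / 90% | 0.968 | 8.07 to 7.82 | 0.704 to 0.734 |
| 60% / 90% | 0.938 | 8.74 to 8.20 | 0.627 to 0.689 |

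If only half the subjects are unprimed (616 v 68), the 70%/90% case goes from 11.46 to 11.09 points and power from 0.388 to 0.413.

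**The case against.** The strongest reply is that nothing planned is wrong. The ANOVAs and the Miettinen-Nurminen intervals are valid, and with equal lots and an SD of 0.8 or less the lot test hardly needs help. That stands, and it limits the size of the point.

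Previous MenACWY vaccination and age are already in the lot model and may absorb part of the baseline correlation. Many unprimed baselines may also sit at half the cut-off (10.1.3.9), which weakens the covariate. Both are fair, and they are why only the within-stratum correlation counts and why 0.5 should not be taken for granted.

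The 5.4.1.4 analyses carry no success criterion and already report GMRs. The first part stands. The second does not replace adjustment, because a GMR fixes the baseline slope at one. With equal SDs the variance of the log change is 2(1 - rho) × SD², for example 1.4 × SD² at rho 0.3, against (1 - 0.09) × SD² = 0.91 × SD² with the covariate.

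For stratification, the gain needs rates that differ between strata and it shrinks as rates approach 100%. The ACWY cells may also be sparse. Both stand, and they make this the weaker half of the point.

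Finally, these methods sit under headings for analyses planned in the protocol, and Section 8 declares no changes, so a change needs to be documented. That is a modest cost.

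**Conclusion.** This is an efficiency improvement, not a bias or type I error problem. The gain from baseline adjustment is real for any non-zero within-stratum correlation: about 2-5% of interval width at rho 0.2-0.3 and 13% at 0.5. It rarely alters the lot conclusion when lots are equal and the SD is at most 0.8 log10. It helps if the SD is near 1.0 or the lots truly differ. Stratifying the 4-fold-rise intervals is worth about 0-6% of width. All these sizes rest on assumed SDs, correlations and stratum rates.

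Three stronger readings are tempting, and the SAP does not support them:

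- **That the 4-fold-rise analyses ignore the randomisation strata.** Section 5.3.1.8 removes one factor by restricting to unprimed subjects, and 5.3.2.8 and 5.4.2.1 use the remaining factors and the same -10% margin. Only the decision interval is unadjusted.
- **That chance baseline imbalance between lots passes in full into the GMT ratio.** It enters through the regression slope, and the ANOVA interval already allows for it. With equal SDs of 0.7 and rho 0.4, an imbalance of one standard error shifts the ratio by 10^(0.4 × 0.7 × 0.0698) = 1.05.
- **That a lot failure would block the other MenABCWY objectives.** Lot consistency is listed first in 5.3.1 and testing is hierarchical, but the order is drawn in Figure 2, which was not available for this check.

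**What to change.** 1. In 5.3.1.7, and in the post-vaccination GMT models of 5.4.1.4, add log10 Day 1 titre for the same serogroup or strain as a covariate. Keep the half-cut-off rule of 10.1.3.9 for values below cut-off.
2. State how a missing Day 1 titre is handled, since 10.1.2.2 does not replace missing results. Without a rule, those subjects drop out of the adjusted model.
3. For 4-fold rise, consider a stratified Miettinen-Nurminen interval as the decision interval (region by age in 5.3.1.8; region by age by previous MenACWY in 5.4.1.1), with the unstratified interval as supportive. Pre-specify how sparse ACWY strata are collapsed. If the unstratified interval is kept for the decision, say why.
4. Record the change in Section 8.

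The cost is SAP wording, one model term and one stratification statement, plus the possible loss of a few subjects without a baseline. No new data are needed.

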#### **5.3.1.8. Immunological non-inferiority: MenABCWY vs. MenACWY**

Analysis set: PPS restricted to subjects without previous ACWY vaccination will be the primary analysis population.

Statistical method: The percentage of subjects with 4-fold rise\*P in hSBA titres against MenACWY indicator strains A, C, W and Y and the corresponding exact two-sided 97.5% CIs based on Clopper-Pearson method will be calculated for the ABCWY (pooled lots) group and the ACWY group [[Clopper, 1934](#)]. The 97.5% CIs for the difference in percentages between ABCWY (pooled lots) and ACWY group will be constructed using the method of Miettinen and Nurminen [[Miettinen, 1985](#)].

Non-Inferiority criterion: Non-inferiority of MenABCWY vaccine for the proportion of subjects with 4-fold rise will be demonstrated if the lower limit of the two-sided 97.5% CI for the difference in percentage of subjects with 4-fold rise between the 2 groups (ABCWY (pooled) lots –ACWY) is above -10%.

\* For the Men A, C, W, Y evaluation, the 4-fold rise is defined as:

- a post-vaccination hSBA titre  $\geq 4$  times the LOD or  $\geq$ LLOQ, whichever is greater, for subjects with a pre-vaccination hSBA titre  $<$ LOD
- a post-vaccination hSBA titre  $\geq 4$  times the LLOQ for subjects with a pre-vaccination hSBA titre  $\geq$ LOD but  $<$ LLOQ, and
- a post-vaccination hSBA titre  $\geq 4$  times the pre-vaccination titre for subjects with a pre-vaccination hSBA titre  $\geq$ LLOQ.

[Table 5](#) reads the LOD and LLOQ of MenACWY indicator strains used in the definition of 4-fold rise provided by the laboratory.

**Table 5 LOD, LLOQ, and ULOQ of MenACWY indicator strains**

Strain	LOD	LLOQ	ULOQ
Men A (3125)	CC1		
Men C (C11)			
Men W (240070)			
Men Y (860800)			

If the co-primary effectiveness objectives for rMenB+OMV NZ are met (Sections 5.3.1.1 through 5.3.1.6), then the above will be evaluated at 95% CI.

#### **5.3.1.9. Vaccine effectiveness (Test-based): MenABCWY**

See Section 5.3.1.1. If the co-primary effectiveness objectives for rMenB+OMV NZ are met (Sections 5.3.1.1 through 5.3.1.6), then the VE for MenABCWY will be evaluated at 95% CI.

#### **5.3.1.10. Effectiveness non-inferiority: MenABCWY vs. rMenB+OMV NZ**

Analysis set: PPS will be the primary analysis population.

Statistical method: The percentage of samples with bactericidal activity measured by enc-hSBA at 1:4 dilution and the corresponding exact two-sided 97.5% CIs based on Clopper-Pearson method will be calculated for the ABCWY (pooled lots) group and the MenB group comparator that will be selected (ref: the footnote of Figure 2). The 97.5% CIs for the difference in percentages between ABCWY (pooled lots) and selected MenB group will be constructed using the method of Miettinen and Nurminen [Miettinen, 1985].

Non-Inferiority criterion: Non-inferiority of MenABCWY vaccine for the percentage of samples with bactericidal activity measured by enc-hSBA at 1:4 dilution will be demonstrated if the lower limit of the two-sided 97.5% CI for the difference between the 2 groups (ABCWY (pooled) lots – MenB) is above -5%.

If the co-primary effectiveness objectives for rMenB+OMV NZ are met (Sections 5.3.1.1 through 5.3.1.6), then the above will be evaluated at 95% CI.

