### 5.3.2.10. Effectiveness non-inferiority: MenABCWY vs. rMenB+OMV NZ

As a sensitivity analysis, a parametric model will be run. A generalized linear model with factors for vaccine group and randomization factors (i.e. region (US/ex-US), age category (10-17 YoA/18-25 YoA), previous MenACWY vaccination (y/n)) will be ran, with the Binary distribution and link function is identity, and outcome is bactericidal activity measured by enc-hSBA at 1:4 dilution. If the lower limit of the two-sided 97.5% CI for the difference in percentage of samples with bactericidal activity measured by enc-hSBA at 1:4 dilution between the 2 groups (ABCWY (pooled) lots –MenB) coming from the model is above -5%, also the sensitivity analysis has demonstrated non-inferiority. If the co-primary effectiveness objectives for rMenB+OMV NZ are met (Sections 5.3.1.1 through 5.3.1.6), then the above will be evaluated at 95% CI.

In addition to the comparison of MenABCWY vs the selected MenB schedule per Section 5.3.1.10, MenABCWY will be compared to the other MenB schedule/schedules, whichever is applicable in the same way as described in Section 5.3.1.10. If MenB 0,2 schedule is selected as comparator, in addition MenABCWY will be compared to Menb 0,6 and MenB 0,2,6 schedule. If MenB 0,6 schedule is selected as comparator, in addition MenABCWY will be compared to MenB 0,2,6 schedule. No success criterion is defined for these group comparisons.

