#### 10.3. Glossary of terms

End of Study (EoS)  (Synonym of End of Trial)	For studies with collection of human biological samples and/or imaging data, the EoS is defined as Last subject last visit (T10). or Last testing results released of samples collected at Visit 6*  * In this case EoS must be achieved no later than 8 months after LSLV.
Primary completion date:	The date that the final subject was examined or received an intervention for the purpose of final collection of data for all primary outcomes, whether the clinical trial was concluded according to the pre-specified protocol or was terminated.
Responder-based vaccine effectiveness:	The enc-hSBA methodology involves testing the serum samples from each individual subject against a subset of around 35 strains randomly chosen from the overall panel of 110 meningococcus B US strains. Responder-based vaccine effectiveness is assessed based on the percentage of subjects considered responders, i.e., subjects whose serum kills the majority ( $\geq 70\%$ in this study) of the tested strains following vaccination.
Test-based vaccine effectiveness:	The enc-hSBA methodology involves testing the serum samples from each individual subject against a subset of around 35 strains randomly chosen from the overall panel of 110 meningococcus B US strains. Test-based vaccine effectiveness is assessed based on the overall percent of individual positive tests following vaccination and represents the reduction in risk compared to the placebo.

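### The primary effectiveness non-inferiority test of MenABCWY vs rMenB+OMV NZ (SAP 5.3.1.10) treats about 35 correlated results per subject as independent, so its nominal error is not held if the correlation is positive

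*SAP*

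**What the plan says.** References are to the current text, SAP Amendment 9.

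- **Primary test, section 5.3.1.10.** Within each group the plan takes "The percentage of samples with bactericidal activity measured by enc-hSBA at 1:4 dilution and the corresponding exact two-sided 97.5% CIs based on Clopper-Pearson method". For the comparison, "The 97.5% CIs for the difference in percentages between ABCWY (pooled lots) and selected MenB group will be constructed using the method of Miettinen" (the Miettinen-Nurminen interval). Success requires a lower limit above -5%. The level becomes 95% if the rMenB+OMV NZ co-primary objectives are met. No allowance for several results from one subject is stated.
- **Unit of the data.** Section 5.3.1.1, on test-based vaccine effectiveness (VE), says: "Each subject will contribute with approximately 35 measures to this analysis". The glossary (10.3) says each serum is tested against "a subset of around 35 strains randomly chosen from the overall panel of 110 meningococcus B US strains".
- **Correlation, section 5.3.1.1.** For the VE model, "a repeated statement will be used to estimate the variance of the RR including correlation within subject's responses to different strains". The code in 5.3.2.1 implements this with subject as the cluster.
- **Sensitivity analysis, section 5.3.2.10.** A generalised linear model with vaccine group and the randomisation factors, "with the Binary distribution and link function is identity, and outcome is bactericidal activity measured by enc-hSBA at 1:4 dilution". No subject or repeated term is stated. The comparisons with the other MenB schedules follow the method of 5.3.1.10.
- **Error control, section 6.** "Full alpha (0.05) is split equally (alpha=0.025) between rMenB+OMV NZ objectives and MenABCWY objectives", with hierarchical testing inside each family.

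**The concern.** Clopper-Pearson and Miettinen-Nurminen intervals are valid for independent Bernoulli observations. Here the observations are serum-by-strain tests, about 35 from one person's serum at one visit. Someone who responds well to the vaccine tends to kill many strains, and someone who responds poorly kills few. Random assignment of strains to subjects does not remove that dependence. The two groups contain different people, so positive within-subject correlation increases the true variance of the difference, and the planned interval ignores the increase.

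The plan accounts for this correlation in one primary analysis and omits it in another that uses the same assay and the same 1:4 cut-off. At stake is a confirmatory claim with a 5-point margin. Section 6 allocates alpha carefully between and within families, and that control fails if one test in the MenABCWY sequence does not hold its level.

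**Working it through.** **Reproducing the plan's sample sizes (section 3.3).** 2×912 + 3×548 + 183 = 3651. With 25% dropout, 912×0.75 = 684 and 548×0.75 = 411. Both match the SAP. Pooled ABCWY is 3×411 = 1233.

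**Results treated as independent.** 1233×35 = 43,155 in ABCWY and 684×35 = 23,940 in the MenB comparator.

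**Nominal one-sided error.** 0.025/2 = 1.25% at the 97.5% CI (z = 2.2414) and 0.05/2 = 2.5% at the 95% CI (z = 1.96).

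**Effect of clustering.** The SAP gives no ICC, so a range is assumed. The design effect is DE = 1 + (35 - 1)×ICC. At a true difference of exactly -5 points, the statistic computed with the independence standard error has standard deviation √DE, so the actual error is P(Z > z/√DE). For ICC 0.10, DE = 4.4 and √DE = 2.10. Then 2.2414/2.10 is about 1.07, which gives 14.3%.

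| Assumed ICC | DE | Error, 97.5% CI (× nominal) | Error, 95% CI (× nominal) |
|---|---|---|---|
| 0.01 | 1.34 | 2.6% (2.1) | 4.5% (1.8) |
| 0.02 | 1.68 | 4.2% (3.4) | 6.5% (2.6) |
| 0.05 | 2.7 | 8.6% (6.9) | 11.6% (4.7) |
| 0.10 | 4.4 | 14.3% (11.4) | 17.5% (7.0) |
| 0.20 | 7.8 | 21.1% (16.9) | 24.1% (9.7) |
| 0.30 | 11.2 | 25.2% (20.1) | 27.9% (11.2) |

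**Simulation check.** The Miettinen-Nurminen score test was applied to pooled tests in 2000 simulated trials per scenario: 1233 vs 684 subjects, 35 of 110 strains each, comparator at 80%, true difference -5 points. Without correlation the error was 0.95% and 2.45%, close to nominal. At ICC of about 0.02, 0.06, 0.11 and 0.24 the inflation was 3.8, 6.8, 13.5 and 19.2 times (97.5% CI) and 2.7, 4.6, 7.7 and 10.9 times (95% CI). This agrees with the formula.

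**When the conclusion would differ.** Assume 85% killing and the 97.5% CI. The independence standard error is √[0.85×0.15×(1/43,155 + 1/23,940)] = 0.00288, and the half-width is about 0.64 points. With clustering it is 1.35 points at ICC 0.10 and 2.16 at ICC 0.30. Both methods agree unless the observed difference lies between about -4.36 and -3.65 (width 1.35 - 0.64 = 0.7) or between about -4.36 and -2.84 (width 2.16 - 0.64 = 1.5), respectively.

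**The case against.** **The unit might be the subject.** A reader could take a sample to be one serum per person. The text does not support that. Section 5.3.1.1 uses the same term with about 35 measures per subject, Table 1 defines this endpoint against each strain, and the glossary describes the test-based measure as a percentage of individual tests. Where a subject-level outcome is wanted, the SAP defines the responder endpoint separately.

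**The size is conditional.** A reader might infer from the table that this plan has 7 to 20 times its nominal error. The documents do not support that as a fact about the trial. It needs an ICC of 0.05 to 0.30, which the SAP does not give, the 97.5% CI, and a true difference exactly at the margin. At the 95% CI the same ICC range gives about 5 to 11 times. The objection to an unconditional multiple stands.

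**Other parts of the plan bear on it.** It is tempting to say that nothing in the plan would expose the problem. Section 5.4.1.3 does summarise each subject's percentage of strains killed, with a 95% CI for the mean. Set beside the pooled within-group interval, it could reveal the understated variance. It is a secondary, within-group output on the full analysis set, so it does not repair the test. Section 5.3.2.10 gives no code for its model. The fair statement is that a subject term is not stated there, not that it is excluded.

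**The practical window is narrow.** This also stands: outside 0.7 to 1.5 points near the margin, on the stated assumptions, both intervals lead to the same conclusion. The within-group intervals carry no success criterion.

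**Conclusion.** The fault is real and should be corrected before analysis. As written, the primary interval in 5.3.1.10 rests on an independence assumption that 5.3.1.1 does not make for the same kind of data, and any positive within-subject correlation breaks the nominal level. The size depends on the ICC. At a true difference of -5 points, error is about 2 to 3 times nominal at ICC 0.01 to 0.02. For ICC 0.05 to 0.30 it is about 7 to 20 times nominal at the 97.5% CI and about 5 to 11 times at the 95% CI. Neither the sensitivity model as worded nor the subject-level summary restores control of the error.

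**What to change.** In 5.3.1.10, base the interval for the difference, and the within-group intervals, on variance clustered by subject. Either of these would do:

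- an identity-link GEE with independence working correlation and robust variance (repeated subject=subject_id). Without covariates this leaves the estimated difference unchanged and alters only its interval;
- a comparison of each subject's proportion of strains killed, with the subject as the unit.

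State the same clustering in the 5.3.2.10 model and in the additional schedule comparisons.

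The cost is SAP wording, a few lines of code and a wider interval. Assuming 80% killing in both groups, the 97.5% half-width rises from 0.72 points to 1.19, 1.52 and 2.42 points at ICC 0.05, 0.10 and 0.30. Power at a true difference of 0 remains high: at ICC 0.30 and the 97.5% CI it is 99.2% with 80% killing and 99.8% with 85%. With 75% killing it would be 97.9%. The killing rates and ICCs are assumptions, since the SAP gives neither.
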